## 1. INTRODUCTION

This statistical analysis plan (SAP) contains definitions of analysis sets, derived variables, and statistical methods for the analysis of efficacy, safety, pharmacokinetics (PK), pharmacodynamics (PD), Immunogenicity and health-related quality of life in the JNJ-77474462PT047 study.

## 1.1. Trial Objectives

#### **Primary Objective**

The primary objective of this study is to evaluate initial efficacy, safety of different dose regimens of bermekimab in adult participants with moderate to severe hidradenitis suppurativa (HS).

## **Secondary Objectives**

The secondary objectives of this study are:

- To evaluate the effect of bermekimab on the dermatologic health-related quality of life in adult participants with moderate to severe HS.
- To evaluate the pharmacokinetics (PK), immunogenicity, and pharmacodynamics (PD) of bermekimab therapy in adult participants with moderate to severe HS.

## 1.2. Trial Design

This is a randomized, double-blind, placebo-controlled study to further establish the efficacy and safety and explore dose effects for bermekimab monotherapy in adults with moderate-to-severe HS. It is anticipated that approximately 50% of patients enrolled will have failed prior targeted biologic therapy(ies) and approximately 50% will be naïve to these forms of biologic therapy in each arm. Patients will be assessed for study eligibility at the initial screening visit after providing informed consent. Thirty days are allowed in the screening window to complete all screening procedures and randomize the participant. During the screening period, certain treatments will be washed out, as applicable, according to eligibility requirements. Patients who fail initially may be re-screened once based on the investigator discretion but only if inclusion criteria are met at time of re-screening.

The study is approximately 40 weeks (30-day screening period, 32-week treatment period and a 4-week follow-up period) for all participants.

A diagram of the study flow (Figure 1) is provided below. Approximately 150 patients who meet eligibility criteria at screening will be randomized in a 1:1:1 fashion to one of three treatment arms:

**Bermekimab 400 mg SC (qw) (Treatment Arm 1)**: 800 mg loading dose of bermekimab (2 x 400 mg SC injections) at weeks 0 and 1 followed by weekly (qw) subcutaneous (SC) injections of 400 mg bermekimab through week 31

**Bermekimab 400 mg SC (q2w) (Treatment Arm 2)**: 800 mg loading dose of bermekimab (2 x 400 mg SC injections) at weeks 0 and 1 followed by subcutaneous (SC) injections of 400 mg bermekimab every other week (q2w) alternating with matching placebo q2w through week 31.

**Placebo (Treatment Arm 3)**: 4mL loading dose of placebo (2 x 2mL SC injections) at weeks 0 and 1 followed by weekly placebo injections from week 2 through week 15. Patients in Arm 3 will begin to receive weekly (qw) blinded subcutaneous (SC) injections of 400 mg bermekimab beginning at week 16 through week 31.

Efficacy assessments (Hidradenitis Suppurativa Clinical Response (HiSCR), Hidradenitis Suppurativa Physician's Global Assessment (HS-PGA), Modified Hidradenitis Suppurativa Score (mHSS), lesion counts, International Hidradenitis Suppurativa Severity Score System (IHS4), Hurley staging, Hidradenitis Suppurativa Symptom Diary [HSSD], Numeric Rating Scale (NRS) for Pain and Itch, Dermatology Life Quality Index [DLQI], Hospital Anxiety and Depression Scale [HADS], Patient's Global Impression of Change [PGI-c], Physician's Global Assessment of Inflammatory Skin Disease (PGA-ISD), Patient Global Impression of Severity (PGI-s), Hidradenitis Suppurativa Quality of Life Measure (HiSQoL), and Health Status Questionnaire (EQ-5D-3L) will be performed according to the Schedules of Activities. Serum samples for PK, immunogenicity, and biomarker analyses will be collected at the timepoints shown in the Study Calendars (Section 5.2 of the protocol).

Blood samples will be collected for laboratory testing including chemistry, hematology, inflammation markers, bermekimab concentration (PK), PD marker(s), and anti-drug antibody.

	Screening	Treatment Period		Follow	
		Baseline	Weekly Dosing	Endpoint Assessment	ronow-up
Visit (V)		V1	V2 to V32	V33	V34
Week (W)	D -30 to -1	W0	W1 to W31	W32	W36
Day (D)		D0	D7 to D217	D224	D252

Figure 1:	Study Flow	Diagram
i igui e i i	Study 1101	Diagram

After completion of the 36-week study period, data will be locked and analyzed for safety and efficacy. In addition to the analyses that will be performed following the formal database lock at the end of the study at Week 36, an additional database lock may be performed at Week 16 to help plan potential future development activities.

## **1.3.** Statistical Hypotheses for Trial Objectives

The primary hypothesis is that bermekimab treatment is superior to placebo as assessed by the proportion of participants achieving Hidradenitis Suppurativa Clinical Response (HiSCR) at Week 12.

• HiSCR is defined as at least 50% reduction in total abscess and inflammatory nodule counts (AN count) with no increase in abscess count and no increase in draining fistula count relative to baseline.

## 1.4. Sample Size Justification

The primary efficacy endpoint is percent of patients who achieve HiSCR at week 12. The sample size is calculated for the bermekimab weekly injection group (Arm 1) versus placebo group (Arm 3) comparison.

Assuming HiSCR is achieved in 60% of intent-to-treat (ITT) patients treated in the bermekimab weekly injection group (Arm 1) versus 30% in placebo treated patients (Arm 3), then, for a randomization ratio of 1:1:1, a sample size of 126 patients (42 in each treatment group) is required for approximately 80% power at a 2-sided 0.05 significance level using Pearson chi-square test. In order to account for possible dropouts and to provide adequate safety data, approximately 150 patients will be randomized and treated.

## 1.5. Randomization and Blinding

## 1.5.1. Procedures for Randomization and Stratification

A centralized block randomization schedule with a 1:1:1 allocation ratio will be utilized using an electronic randomization system. Patients will be randomly assigned to Arms 1, 2, or 3. The randomization schedule will be stratified by two factors: prior biologic use (yes/no) and Hurley Stage (II/III).

## 1.5.2. Maintenance of Blind

The study blind will be maintained for the duration of the study, until after the Final (Week 36) DBL.

In order to maintain blinding, all patients will receive two injections at week 0 and 1, followed by weekly injections from weeks 2 to 31. Additionally, to ensure that no unintentional unblinding occurs during study drug administration, at least one qualified individual will be designated at each study site to perform all preparation and injection of the investigational product. The designated injector(s) should have no other contact with the participant during the study, should not discuss the participant's treatment with the participant, participant's caregiver, or other site personnel at any time, and will not be permitted to review the participant's medical records, questionnaires, or the electronic CRF prior to each injection. The designated injector(s) should be documented in the source documents at each visit.

The investigator will not be provided with randomization codes. The codes will be maintained within the Electronic Data Capture (EDC) system, which has the functionality to allow the investigator to break the blind for an individual participant.

Data that may potentially unblind the intervention assignment (ie, study intervention serum concentrations, anti-bermekimab antibodies, and intervention allocation) will be handled with special care to ensure that the integrity of the blind is maintained and the potential for bias is minimized. This can include making special provisions, such as segregating the data in question from view by the investigators, clinical team, or others as appropriate until the time of DBL and unblinding.

Under normal circumstances, the blind should not be broken until all participants have completed the study and the database is finalized. However, a number of prospectively identified Sponsor individuals will be unblinded at the Week 16 DBL for the purposes of performing data analysis and review. Identification of sponsor personnel who will have access to the unblinded data at participant-level and who will have access to the unblinded data at group-level will be documented prior to unblinding at the Week 16 DBL. All site personnel and participants will remain blinded to the treatment assignments until the last participant completes Week 36 evaluations and the database has been locked.

In the event of an emergency that would require the investigator to be aware of the treatment allocation prior to the end of the trial, the investigator can obtain this information, on a per participant basis, after consultation with the Sponsor's Medical Monitor, if possible. Every effort should be made to consult with the Medical Monitor prior to emergency unblinding. Events that qualify as emergencies are as follows:

- A grade 3 or greater AE which are "probably or definitely" related to study drug, and only if treatment assignment information is essential for the management of the event. This type of reaction would require that the patient receives no further doses, and is followed until the resolution of the toxicity.
- Any suspected, unexpected, serious adverse reaction (SUSAR)
- Pregnancy

The investigator may, in an emergency, determine the identity of the intervention through EDC system. While the responsibility to break the intervention code in emergency situations resides solely with the investigator, it is recommended that the investigator contact the sponsor or its designee if possible to discuss the particular situation, before breaking the blind. Telephone contact with the sponsor or its designee will be available 24 hours per day, 7 days per week. In the event the blind is broken, the sponsor must be informed as soon as possible. The date and reason for unblinding must be documented in the appropriate section of the eCRF, and in the source document. The documentation received from the EDC indicating the code break must be retained with the participant's source documents in a secure manner.

Participants who have had their intervention assignment unblinded by the investigator will not be eligible to receive further study intervention, but should continue to complete early termination visit specified in the Study Calendars section (section 5.2 of the protocol).

## 2. GENERAL ANALYSIS DEFINITIONS

This analysis plan provides the general analysis definitions and describes the planned subject information, efficacy, safety, pharmacokinetics, and antibody analyses for the two planned DBLs.

## 2.1. Imputation Rules for Partial or Missing AE Dates

Partial AE onset dates will be imputed as follows:

- If the onset date of an adverse event is missing day only, it will be set to:
  - First day of the month that the AE occurred, if month/year of the onset of AE is different than the month/year of the study agent start
  - The day of study agent start, if the month/year of the onset of AE is the same as month/year of the study agent start date and month/year of the AE resolution date is different
  - The day of study agent start or day of AE resolution date, whichever is the earliest, if month/year of the onset of AE and month/year of the study agent start date and month/year of the AE resolution date are same
- If the onset date of an adverse event is missing both day and month, it will be set to the earliest of:
  - January 1 of the year of onset, as long as this date is on or after the study agent start date
  - Month and day of the study agent start date, if this date is in the same year that the AE occurred
  - Last day of the year if the year of the AE onset is prior to the year of the study agent start date,
  - The AE resolution date.
- Completely missing onset dates will not be imputed.

Partial AE resolution dates not marked as ongoing will be imputed as follows:

- If the resolution date of an adverse event is missing day only, it will be set to the earliest of the last day of the month of occurrence of resolution or the date of death, if the death occurred in that month.
- If the resolution date of an adverse event is missing both day and month, it will be set to the earliest of December 31 of the year or the day and month of the date of death, if the death occurred in that year.
- Completely missing resolution dates will not be imputed.

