## 2.4.2. Safety Analysis Set

The safety analysis set includes all randomized participants who received at least 1 dose of study agent, i.e., the treated population.

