## Summaries through Week 16 (placebo controlled):

Safety data through Week 16 will be summarized by treatment groups

- 1. Placebo
- 2. Bermekimab 400 mg q2w
- 3. Bermekimab 400 mg qw
- 4. Combined Bermekimab

This allows between-group comparisons of safety between the bermekimab regimens and the placebo group based on similar follow-up period in each group.

#### Summaries through Week 36

Safety data through Week 36 will be summarized by treatment groups including

- 1. Placebo  $\rightarrow$  bermekimab 400 mg qw
- 2. Bermekimab 400 mg q2w
- 3. Bermekimab 400 mg qw
- 4. Combined Bermekimab

This allows safety comparisons between each bermekimab regimen through Week 36 based on the similar follow-up time in each group.

The list of actual treatment groups for safety analyses and inclusions of participants and safety events/measurements in each group are defined as follows:

- 1. **Placebo:** all participants who were randomized to placebo at Week 0 and received treatment with placebo only or received treatment with placebo prior to receiving treatment with bermekimab. For participants who started treatment with placebo but later received bermekimab, the safety events/measurements on and after the first dose of bermekimab will be excluded from this group. Only the safety events/measurements that occurred while the participants had been receiving placebo only will be included in this group.
- Placebo → bermekimab 400 mg qw: All participants who were randomized to placebo at Week 0 started treatment with placebo only and later crossed over to receive treatment with bermekimab 400 mg SC (qw). Only the safety events/measurements from these participants that occurred on and after their first administration of bermekimab will be included in this group.
- 3. **Bermekimab 400 mg q2w:** all participants who were randomized to bermekimab 400 mg SC (q2w) at Week 0 and received bermekimab. All the safety events/measurements from these participants that occurred from Week 0 will be included in this group.
- 4. **Bermekimab 400 mg qw:** all participants who were randomized to bermekimab 400 mg SC (qw) at Week 0 and received bermekimab. All the safety events/measurements from these participants that occurred from Week 0 will be included in this group.

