## 6.1. Adverse Events

The verbatim terms used in the eCRF by investigators to identify adverse events will be coded using the Medical Dictionary for Regulatory Activities (MedDRA). Any AE starting at or after the initial administration of study agent through the end of the trial is considered to be treatment emergent. If the event occurs on the day of the initial administration of study agent, and either event time or time of administration are missing, then the event will be assumed to be treatment emergent. If the event date is recorded as partial or completely missing, then the event will be considered to be treatment emergent unless it is known to be prior to the first administration of study agent based on partial onset date or resolution date. All reported treatment-emergent adverse events will be included in the analysis.

The following analyses will also be used to assess the safety of participants in the study:

- The incidence and type of AEs.
- The incidence and type of SAEs.

- AEs of severe intensity
- AEs that led to permanent discontinuation of study agent administration
- The incidence and type of reasonably related AEs.

In addition, a participant who had injection site reaction(s) in 30 minutes (+/-10) post injection at Weeks 0, 1, and 2 were recorded in eCRF. The incidence of injection-site reaction during this time frame will be summarized.

These summary tables will provide the count and percentage of participants with 1 or more of the specified AEs by treatment group. In addition to the summary tables, listings will be provided for participants who:

- Had SAEs.
- Had AEs leading to discontinuation of study.
- Had AEs of severe or life threating, or fatal based on CTCAE (grade  $\geq$ 3) intensity.
- Had anaphylactic or serum sickness-like reactions.

Since safety should be assessed relative to exposure and follow-up, most AE summary tables will include average weeks of follow-up and average number of study agent administrations, infusions and injections for each treatment group. A listing of participants who died will be provided.

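### Partial AE onset dates are anchored only to study agent start, so Arm 3 events with a missing day in the crossover month are counted under placebo even if they began on bermekimab

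*SAP*

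**What the plan says.** SAP 2.1 uses one treatment date, the start of study agent. With only the day missing, onset becomes the "First day of the month that the AE occurred, if month/year of the onset of AE is different than the month/year" in which study agent began; within the start month it goes to the start date, or to the resolution date if that is earlier. With day and month missing, onset is the earliest of several candidates, among them 1 January of the onset year and "Month and day of the study agent start date, if this date is in the same year that the AE occurred". For the rest, "Completely missing onset dates will not be imputed". No branch uses the first bermekimab dose.

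Study agent includes placebo: the safety set in SAP 2.4.2 is "all randomized participants who received at least 1 dose of study agent, i.e., the treated population". Arm 3 receives placebo from Week 0 and, under SAP 1.2, "injections of 400 mg bermekimab beginning at week 16 through week 31".

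SAP Section 6 divides Arm 3 events at that switch. The Placebo column excludes anything on or after the first bermekimab dose. For the Placebo→bermekimab column, "Only the safety events/measurements from these participants that occurred on and after their first administration of bermekimab will be included in this group". Arms 1 and 2 count all events from Week 0.

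SAP 6.1 adds: "If the event date is recorded as partial or completely missing, then the event will be considered to be treatment emergent". The one exception is an event shown to predate the first study agent. That settles treatment-emergent status, not the choice between the two Arm 3 columns.

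**The concern.** Arm 3 has two boundaries that matter for safety: first study agent and first bermekimab. The imputation rule protects only the first. At Week 0 a day-missing event is resolved toward treatment, which is conservative. At Week 16, where placebo ends and drug begins, the same kind of event is resolved toward placebo.

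The stake is the Placebo→bermekimab column of the Week 36 safety tables. On-drug events that lack a day in the crossover month leave that column, whereas Arms 1 and 2 lose none of theirs. There is also a gap in the specification: an Arm 3 event with no onset date at all is declared treatment emergent but has no rule that places it in either column.

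**Working it through.** The plan states no figure on this point, so there is none to reproduce. The check applies the rule as written.

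**Inputs.** The imputation rule is from SAP 2.1 and the column rule from SAP Section 6. Crossover is at day 112 ± 3 (protocol 5.1, Visit 17). Two assumptions are mine: Week 0 dates run over the calendar years 2020 and 2021 (731 dates), and true onset is uniform over the days of the crossover month. With 7 possible crossover offsets (days 109 to 115), there are 731 × 7 = 5,117 combinations.

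**Step 1: which branch applies.** In none of the 5,117 combinations is crossover in the same calendar month as study agent start; it is always 3 or 4 months later. The day-1 branch therefore always governs.

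**Step 2: where Arm 3 day-missing events go.**
- Crossover falls on the 1st in 3.3% of combinations; only then does day 1 not precede the first bermekimab dose.
- Share sent to Placebo: 100% − 3.3% = about 97%.
- Share that truly began on or after first bermekimab: about 52%.
- Of those on-drug events, about 94% are placed under Placebo.
- Share of all such events in the wrong column: 0.516 × 0.936 = 0.483, about 48%.

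Example: Week 0 on 16 March 2020 gives crossover on 6 July 2020. An event that began on 20 July but is recorded only as July 2020 becomes 1 July and is counted under Placebo.

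**Step 3: day and month missing.** Take an onset year equal to the crossover year and no earlier resolution date. With crossover at day 112, the imputed date precedes crossover for 729 of 731 start dates.

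**Step 4: Arms 1 and 2.** The day-1 rule is not specific to Arm 3. Let X be the number of day-missing events per arm in the Week 16 month, assumed equal across arms. Of these, about 1 − 0.52 = 0.48 truly precede the Week 16 dose. Ignoring resolution dates, the through-Week-16 table receives:

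| Rule | Arm 3 (Placebo) | Arm 2 | Arm 1 |
|---|---|---|---|
| SAP as written | about X | about X | about X |
| Week 16 anchor in Arm 3 only | about 0 | about X | about X |
| Week 16 anchor in all arms | about 0 | about 0 | about 0 |
| True content | about 0.48X | about 0.48X | about 0.48X |

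**Step 5: effect of a Week 16 anchor in Arm 3.** On-drug events wrongly under Placebo fall from about 94% to 0%. All pre-crossover day-missing events in that month now go to Placebo→bermekimab: 1 − 0.516 = 0.484. Total misclassification is about 48% before and after.

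**Step 6: number of events.** Expected mislabelled = crossovers × AEs per patient in that month × share with day missing × about 0.5. One third of 150 is 50 patients in Arm 3. I assume 40 to 50 cross over, 0.3 to 1.0 AE each in that month, and 2% to 10% with the day missing; the documents give none of these.
- Low: 40 × 0.3 × 0.02 × 0.5 = 0.12
- High: 50 × 1.0 × 0.10 × 0.5 = 2.5

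**The case against.** A reader might infer that the error always favours the drug, including in the main safety comparison. The documents do not support that. SAP Section 6 makes the through-Week-16 table the one for comparing bermekimab with placebo, and there the day-1 rule adds events to all three columns alike. The one-way error is confined to the Placebo→bermekimab column. For the same reason, a correction in Arm 3 alone would create an imbalance that the present rule does not have.

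A reader might also infer that reactions to the first active doses would be hidden. That is the least likely case. Protocol 5.1 and Section 7 require on-site observation and AE assessment about 30 minutes after injection at Visits 17, 18 and 19. Grade 3 or higher events and serious events must reach the sponsor within 24 hours of awareness. Such events will rarely lack a day. The SAP 6.1 summary of post-injection reactions does cover only Weeks 0, 1 and 2, so Arm 3's first active doses depend on the ordinary date split, but this does not make their dates incomplete.

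Three further points stand. AEs are reviewed at weekly visits, so partial dates should be few. The tables carry no formal comparison. And the SAP never says outright that imputed dates decide the column; that is inferred, because Section 6 assigns by time of occurrence and SAP 2.1 is the only rule that supplies a date.

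None of this removes the core point. A written rule sends on-drug events to placebo, and no other rule corrects it.

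**Conclusion.** The point holds in limited form. SAP 2.1 has no anchor at first bermekimab, so about 97% of Arm 3 day-missing events in the crossover month go to Placebo, although about 52% would have begun on drug under uniform onset. The Placebo→bermekimab column is understated. The through-Week-16 table is inflated in every arm and is not tilted toward the drug, provided such events are about equally frequent across arms.

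The likely count is small: about 0.1 to 2.5 events, resting wholly on assumed rates. Efficacy is untouched. For completely missing onsets the gap is one of wording, and no frequency can be estimated. This is a cheap improvement, not a threat to the trial's conclusions.

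**What to change.** Add a second anchor to SAP 2.1 for all three arms. If the onset month and year equal those of the Week 16 dose (in Arm 3, the first bermekimab dose) and the day is missing, set onset to that dose date unless the resolution date is earlier. Participants who never receive that dose stay under the present rule.

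In Arm 3, follow the same principle when day and month are both missing, or when onset is completely missing: count the event under Placebo→bermekimab unless it is known to precede the first bermekimab dose.

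State that the through-Week-16 table stops before the Week 16 dose in every arm. The SAP says this only for Placebo, and without it the re-anchored events could stay in the Arm 1 and Arm 2 columns.

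The cost is a few SAP sentences and a few lines of programming, with no new data. The downside should be stated openly: under uniform onset, about as many true placebo-period events move to Placebo→bermekimab as on-drug events are recovered, so total misclassification does not fall. What is gained is a residual error that is conservative for the active drug, as at Week 0, with the through-Week-16 comparison kept balanced for day-missing events. That balance does not extend to events lacking both day and month, or the whole date, where only Arm 3 changes.
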